The following criteria should be met to define UTI: 1. Symptoms of dysuria, urgency, frequency, or hematuria, fever, flank pain, nausea/vomiting; AND 2. Pyuria and/or bacteriuria²⁶. The following criteria should be met to define sepsis: 1.Temperature >38°C or <36°C Heart rate >90/min Respiratory rate >20/min, PaCO2 <32 mm Hg (4.3 kPa), White blood cell count >12 000/mm3 or <4000/mm3 or >10% immature bands, or evidence of organ failure; AND 2. urinary pathogen growth in urine or blood cultures²⁷. The EAU classifies UTI as Localised or Systemic. Localised UTI is defined as signs and symptoms of frequency, urgency, Incontinence, urethral purulence, and suprapubic pain, which applies to both sexes, and with no signs of systemic infection. Systemic UTI is defined as signs and symptoms of systemic infection such as fever or hypothermia, chills, Delirium, Hypotension, Tachycardia, and Costovertebral angle pain and tenderness. Pyelonephritis and prostatitis are included in this classification.

The prevalence of Prostatitis is 8.2%. Prostatitis is classified into four clinical entities including acute bacterial prostatitis, chronic bacterial prostatitis, chronic pelvic pain syndrome and asymptomatic prostatitis. Diagnostic evaluation includes history and physical examination, urinalysis, urine gram stain and culture, pre- and post-prostatic massage, and Prostate specific Antigen. Complete Blood Count, Blood culture is not routinely done, but may be necessary in a patient who appears ill²⁸.

Acute Bacterial prostatitis is defined as bacterial infection of the prostate which may lead to overwhelming sepsis or development of prostatic abscess. An organism must be isolated on culture. Most commonly isolated organism is E. Coli. Diagnosis is based on symptoms alone which include irritative and/or obstructive symptoms. Pain and systemic symptoms may be present as well. On physical examination, prostate appears boggy, tender, and enlarged. Diagnosis is made through a urinalysis and urine culture. Presence of more than 10 WBCs per hpf suggests a positive diagnosis. It is usually treated with antibiotcis²⁸.

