Chronic Bacterial Prostatitis is a bacterial infection of the prostate lasting more than 3 months. Urine cultures are persistently positive for the same organism. E. coli is still the most common organism isolated. Patients present with recurrent or relapsing urinary tract infections, urethritis, or epididymitis with the same bacterial strain. Diagnosis is made through history or physical examination, Voiding test such as pre and post prostatic massage and a positive urine culture²⁸.

Asymptomatic prostatitis is diagnosed when inflammatory cells are identified incidentally on prostate biopsy on an asymptomatic patient. Treatment is catered based on the primary reason for urologic consultation. Further urologic evaluation is indicated if the reason for consult is an increased PSA²⁸.

Preoperative antibiotic prophylaxis is the administration of antibiotics before surgery to reduce the risk of post operative infection. Although the timing of antibiotic administration varies, the goal of preoperative systemic antibiotic prophylaxis is to maintain the highest tissue concentrations at baseline and during surgery. The literature recommends at least 30 minutes and no more than 60 minutes before skin incision to achieve the optimal time for preoperative administration of the most commonly used antibiotics²⁹.

Post biopsy infection is the Occurrence of Lower Urinary tract Infection symptoms such as frequency, dysuria, and urgency, or Severe Urinary Tract Infection such as loin pain, rigour and fever³. Microbiologic tests include a positive urinalysis, and urine culture. Occurrence of urosepsis, meeting a SOFA score of > 2 in the presence of a urinary tract pathogen, all of which occurring within 2 weeks post biopsy.

Objectives

General Objective

To compare incidence infectious complications in patients given antibiotic prophylaxis versus no prophylaxis among patients at St. Luke's Medical Center Global City and Quezon City from March 2024- January 2024

Specific Objective

- 1. To compare the incidence of urinary tract infection and sepsis between patients without and with antibiotic prophylaxis undergoing prostate biopsy.
- 2. To compare Hospital admissions, Emergency room visits, and non-infectious complications between the no prophylaxis versus prophylaxis groups.

Methods

Study design and setting

This will be a randomized controlled trial to be conducted at St. Luke's Medical Center Global City and Quezon City from June 2024 to June 2025.

Study population

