Patients experiencing an adverse event such as symptoms of urinary tract infection like hematuria, dysuria, frequency, and urgency and systemic symptoms such as fever, generalized weakness, malaise will be evaluated right away initially with a complete blood count, urinalysis, and urine culture. Patients who will satisfy the criteria of Urinary Tract Infection, will be considered as having post biopsy infectious complications, and will be evaluated for possible sepsis. According to literature, 2% of patients undergoing prostate biopsy may experience mild post biopsy infection. 1% of patients may develop severe infections or urosepsis requiring hospitalization²². Computed sample size for the study is a total of 120 patients, with 60 patients in each arm. Hence, if more than 2 patients develop mild biopsy infection, and more than 1 patient develop severe infections from the experimental group, the study will be terminated and conclusion will be recommendation of administration of antibiotic prophylaxis. Patients who were not able to complete the procedure due to any circumstance, those who cannot tolerate anesthesia, those with adverse effects from anesthesia or antibiotics, and patients not compliant to follow up tests will be withdrawn from the study.

Data to be gathered

Patients who will pass the inclusion criteria will have their demographic data recorded such as age, sex, Height, Weight, BMI, Charlson Scores, Prostate volume, PSA, and History of Previous Biopsies. Post operatively, UTI will be assessed using a symptom checklist, which includes dysuria, urgency, frequency, or hematuria, fever, flank pain, nausea/vomiting. Signs of Systemic Inflammatory Response Syndrome (SIRS) will be gathered in patients who develop signs of urinary tract infection, namely, Temperature, Heart Rate, Respiratory Rate, White Blood Cell Count, and Blood Pressure. Incidence of sepsis and UTI In both groups will be recorded. Patients with Fever, or 2 or more signs of SIRS will be advised admission immediately. Histopathology results, 30 day readmissions, 30 day emergency room visit, and non infectious complications based on the Clavien Dindo classification will also be gathered.

Laboratory/assessment procedures to be performed

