Patients with adverse effects will be followed until resolution or stabilization. A cut-off of 30 days was chosen because the vast majority of post-biopsy infections will occur within this time period. A standard data collection form will be used and information will be recorded in a password protected Excel spreadsheet. Any time post biopsy, patients may call the primary investigator to have them properly assessed and advised, in coordination with consultants on board the study, and possible a referral to infectious disease service for treatment planning. Treatment costs will be shouldered by the study as part of indemnification. A budget proposal will be submitted to cover for treatment costs. For patients with mild symptoms which may be treated as outpatient, a budget of 10,000 pesos per patient will be given.

[figure not shown]
Description of Outcome Measures

Primary outcome is the incidence of Urinary tract infection and Sepsis. Urinary tract infection is based on the European Association of Urology guidelines on infection. Localized UTI is defined as having symptoms of Dysuria, Urgency, Frequency, Incontinence, and Pressure or cramping in the lower abdomen. Systemic UTI is defined by the presence of localized symptoms plus one of the following: Fever or hypothermia, Rigors, shaking or chills, Delirium, Hypotension, Tachycardia, and Costovertebral angle pain and tenderness. Mild, and Self-limiting lower urinary tract symptoms such as hematuria and dysuria which spontaneously resolves will not be assessed as urinary tract infection, as these are commonly seen after prostate biopsy and rarely require treatment.

Secondary outcome includes the following: 30 day hospital admissions, 30 day emergency room visits, and non-infectious complications such as acute urinary retention will be recorded.

Sample Size and Sampling Technique

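### Non-urinary biopsy infections fall under no infection endpoint, although the title and general objective cover infectious complications as a whole

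*Protocol*

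**What the plan says.** The general objective is broad: "To compare incidence infectious complications in patients given antibiotic prophylaxis versus no prophylaxis". The title likewise speaks of post-procedural infections. Specific objective 1 is narrower: "To compare the incidence of urinary tract infection and sepsis between patients without and with antibiotic prophylaxis undergoing prostate biopsy". The primary outcome follows the specific objective: "Primary outcome is the incidence of Urinary tract infection and Sepsis".

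The definitions are mainly urinary. In Description of Outcome Measures, localized UTI is a list of lower urinary tract symptoms, and "Systemic UTI is defined by the presence of localized symptoms plus one of the following", the list being systemic signs. That section does not define sepsis. The Background definition requires "urinary pathogen growth in urine or blood cultures" in addition to clinical signs, and the Background description of post-biopsy infection includes urosepsis, defined as "meeting a SOFA score of > 2 in the presence of a urinary tract pathogen".

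The secondary outcomes are admissions and emergency room visits to day 30, whatever their cause, plus non-infectious complications. Data to be gathered confirms the last item: "non infectious complications based on the Clavien Dindo classification will also be gathered". The post-operative symptom checklist described there is for UTI and lists urinary and systemic symptoms. The scheduled tests at day 7 are urinalysis and urine culture.

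**The concern.** The Introduction describes the route under study as a needle passed through the perineal skin, and the procedure section has that skin shaved, prepared and cleaned in every patient. Infection at the puncture site is therefore a complication of this route, and one that an intravenous antibiotic given beforehand could plausibly affect. Yet it is neither a UTI nor, without a urinary pathogen, sepsis as the Background defines it. Nor can it be entered as a non-infectious complication.

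The trial could then report that omitting prophylaxis is non-inferior for infectious complications without having compared the arms on one group of them. The general objective would be only partly answered.

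**Working it through.** **1. The plan's own figure.** Inputs from Sample Size and Sampling Technique: infection rates of 1.35% with and 1.22% without prophylaxis, a margin of 5 percentage points, 80% power and a 90% interval (one-sided alpha 0.05).

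n per arm = (1.645 + 0.842)² × [0.0135 × 0.9865 + 0.0122 × 0.9878] / (0.05 + 0.0013)² = 6.183 × 0.02537 / 0.002632 = 59.6, rounded up to 60.

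The stated 60 per arm is reproduced. The source rates are for genitourinary infections, so the sample size fits the narrow primary outcome.

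**2. Where different infections would be recorded.**

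| Event after biopsy | Primary outcome | Secondary outcomes |
|---|---|---|
| Persistent dysuria and frequency from bladder infection | Yes, localized UTI | Only if admitted or seen in the emergency room |
| Prostatitis or pyelonephritis with urinary symptoms and fever | Yes, systemic UTI | As above |
| Prostatitis with fever but no localized symptoms | Yes by the Background text, no by the Outcome Measures wording | As above |
| Perineal skin infection or abscess, no urinary symptoms, managed in clinic | No | None: the complication category is non-infectious |
| The same, leading to admission or an emergency room visit | No | Yes, but not identified as an infection |
| Epididymo-orchitis without urinary symptoms | No by the Outcome Measures wording | Only if admitted or seen in the emergency room |

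The fourth row enters no listed outcome. The last three rows are not infection endpoints under the Outcome Measures wording.

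**3. How far single events matter.** Expected events per arm are 60 × 0.0135 = 0.81 and 60 × 0.0122 = 0.73. The simple upper 90% bound for no prophylaxis minus prophylaxis is d + 1.645 × √[p₁(1−p₁)/60 + p₂(1−p₂)/60], to be compared with 5%:

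- 1 v 0: 1.67% + 1.645 × 1.65% = 4.39% (met)
- 2 v 0: 3.33% + 1.645 × 2.32% = 7.15% (not met)
- 1 v 1: 0 + 1.645 × 2.34% = 3.84% (met)
- 2 v 1: 1.67% + 1.645 × 2.85% = 6.35% (not met)

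With the Newcombe (Wilson-score) interval, 0 v 0 gives 2.706 / (60 + 2.706) = 4.3% (met) and 1 v 0 gives 7.13% (not met). In each pair, one more infection in the no-prophylaxis arm changes the conclusion. This would be true of any reclassified event. It shows how fragile 60 per arm is, not how many infections the definitions leave out.

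**4. What widening the primary outcome would cost.** The documents give no rate for non-urinary infection. As an assumption, add a rate x equally to both arms in the formula of step 1:

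| Assumed x | n per arm for 80% power | Power at 60 per arm | Chance of at least one such event in 120 patients, 1 − (1−x)¹²⁰ |
|---|---|---|---|
| 0.25% | 72 | 74% | 26% |
| 0.5% | 83 | 68% | 45% |
| 1% | 105 | 59% | 70% |
| 2% | 150 | 47% | 91% |

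Widening the primary outcome therefore disturbs the sample size. A secondary outcome does not.

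**The case against.** The strongest reply is that the protocol is consistent about a urinary endpoint. The Background description of post-biopsy infection, specific objective 1, the primary outcome and the planning rates all agree, and only the title and a loosely worded general objective are wider. That stands. Choosing UTI and sepsis as the primary outcome is defensible, and the point is not that the primary outcome is wrong.

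A reader might infer that other infections count nowhere. The documents do not support that. Admissions and emergency room visits are secondary outcomes without restriction on cause, and the Background places pyelonephritis and prostatitis under systemic UTI. The Background's general UTI criteria also accept fever or flank pain together with pyuria or bacteriuria, so some cases without lower urinary tract symptoms could qualify there.

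A febrile perineal abscess treated as an outpatient is not a safe example either. Data to be gathered advises admission for fever, although that sentence follows text about patients with signs of UTI, and Follow-up procedures allows outpatient care for some patients with fever and urinary symptoms. Those passages need reconciling, but this point does not depend on how.

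Nor would such infections necessarily go unseen. There is a history and physical examination at day 7, patients are asked to report symptoms of infection to day 30, and Ethical Considerations adds teleconsults at 24 and 48 hours. The data collection form is not shown, so it cannot be said to lack perineal items. What remains is that no stated outcome would class the finding as an infection.

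**Conclusion.** The point holds in a limited form. Non-urinary biopsy infections are in no infection endpoint, and one that leads to neither admission nor an emergency room visit is in no listed outcome at all. The mismatch is with the title and general objective, not with specific objective 1. It rests on reading the Outcome Measures wording for UTI and the Background wording for sepsis as the operative definitions.

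The size cannot be given, because the documents contain no rate for these infections. A reader might infer from the interval figures that the result is biased toward non-inferiority. They do not show this. An uncounted infection in the prophylaxis arm would move the result the other way, and the documents offer no evidence of an effect at the puncture site. The supportable statement is that a harm there could be missed. It is worth correcting because the remedy is cheap.

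**What to change.** Keep UTI and sepsis as the primary outcome and keep 60 per arm. Then:

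- Add *other biopsy-related infection within 30 days* as a secondary outcome compared between arms, defined to include perineal skin or soft-tissue infection or abscess and epididymo-orchitis not meeting the UTI definition.
- Under the Clavien-Dindo item, and wherever it is repeated, replace non-infectious complications with all complications.
- Record perineal and scrotal signs at the existing day-7 history and examination, and in symptom reports to day 30.
- State that a non-inferiority conclusion applies to UTI and sepsis, not to all infections.

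This needs no extra visit or test. The downside is a few more items to record and a secondary outcome with very few events: even 0 v 0 leaves a Newcombe upper 90% bound of 4.3%, so it can describe but hardly exclude a difference. If the sponsor prefers to widen the primary outcome, the sample size must be recalculated with a justified rate.

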All patients will be followed for 30 days for and assessed for post procedure infection. Initial assessment will be at 7 days post operatively with a history and physical exam. Symptoms of Urinary tract infection will be recorded. Urinalysis and urine culture will also be taken this time. Patients who are asymptomatic will be followed for 30 days, and will be asked to report symptoms of infection. All events within 30 days such as hospital admissions, emergency room visits, and non-infectious complications such as acute urinary retention will be reported. Mild and self limiting lower urinary tract symptoms, and hematuria will not be recorded as urinary tract infection as these are commonly seen after prostate biopsy. Patients who remain asymptomatic after the 30th post operative day will be treated as not having a post procedural infection. Persistent and severe lower urinary tract symptoms with associated fever will be assessed as having developed a post procedural infection, and patients will be treated accordingly. For patients who report symptoms on initial assessment, or within the 30 day time period, patients will be asked to contact primary investigator immediately for assessment, and will be asked to do a baseline Complete Blood Count, Urinalysis, and Urine Culture. Patients with mild to moderate illness (symptoms of fever and lower urinary tract symptoms such as those mentioned above, without urosepsis, circulatory failure and/or organ dysfunction may be treated as outpatient. Patients will be started on Ciprofloxacin 500mg 2x a day for 4 weeks, in line with recommendations of the European Association of Urology on treating Acute Prostatitis. Patients with marked debility and signs of sepsis as mentioned above, patients in whom there is uncertainty in diagnosis, and patients in whom there is concern about adherence to treatment, or patients unable to maintain oral hydration, or take oral medications, are patients in whom hospitalization will be advised. Baseline Complete Blood Count, Creatinine, Urinalysis, Urine Culture and Sensitivity and additional Blood culture and sensitivity will be done. Patients will be admitted in the private room of the hospital, and will be started on Broad Spectrum Antibiotics. Other additional medical management may vary depending on signs, symptoms and culture results. Hospital stay may vary as well, depending on signs and symptoms.

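### The primary-outcome definition makes localized urinary symptoms a condition for systemic UTI, contradicting the same EAU classification as the protocol reports it in its Background section

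*Protocol*

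**What the plan says.** Description of Outcome Measures sets the endpoint: "Primary outcome is the incidence of Urinary tract infection and Sepsis". It names its source: "Urinary tract infection is based on the European Association of Urology guidelines on infection". Two categories follow.

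- Localized: "Localized UTI is defined as having symptoms of Dysuria, Urgency, Frequency, Incontinence, and Pressure or cramping in the lower abdomen". Fever and flank pain are not in this list.
- Systemic: "Systemic UTI is defined by the presence of localized symptoms plus one of the following: Fever or hypothermia, Rigors, shaking or chills", with further systemic signs after these. Localized symptoms are a condition, not an alternative.

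Other sections describe the event differently.

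- Background, EAU classification: "Systemic UTI is defined as signs and symptoms of systemic infection such as fever or hypothermia, chills, Delirium, Hypotension, Tachycardia". No localized symptom is required, and the text adds: "Pyelonephritis and prostatitis are included in this classification".
- Background, first UTI definition: a symptom list that includes fever and flank pain, together with pyuria and/or bacteriuria.
- Background, post-biopsy infection: lower urinary symptoms, "or Severe Urinary Tract Infection such as loin pain, rigour and fever".
- Data to be gathered: the postoperative UTI checklist includes fever and flank pain beside the bladder symptoms.
- Follow-up procedures: "Persistent and severe lower urinary tract symptoms with associated fever will be assessed as having developed a post procedural infection".

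Sample Size and Data Analysis give 60 per group, assumed infection rates of 1.35% with and 1.22% without prophylaxis, and non-inferiority if the upper 90% confidence bound is below 5%.

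**The concern.** Two sections appeal to the same guideline and use the same term, but they define different sets of cases. The stricter version is in the section that defines the primary outcome. The cases it excludes are febrile infections without bladder symptoms, which are among the more serious events a trial of omitting prophylaxis needs to count.

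In a non-inferiority trial, under-counting events in both arms is not conservative. It pulls a true excess towards zero and narrows the interval, and both make non-inferiority easier to declare. With so few events expected, the classification of one patient can matter.

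**Working it through.** **1. Who is affected.** Take a man with fever, rigors and costovertebral pain a few days after biopsy, and no bladder or lower-abdominal symptoms.

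| Definition | Counted? |
|---|---|
| Outcome Measures, localized UTI | No |
| Outcome Measures, systemic UTI | No, localized symptoms absent |
| Background, EAU systemic UTI | Yes |
| Background, first UTI definition | Yes, if pyuria or bacteriuria is present |
| Background, post-biopsy infection | Yes on symptoms (microbiological tests and a 2-week window are also named) |
| Background, sepsis by SIRS-type signs | Only with urinary pathogen growth in urine or blood |
| Background, urosepsis by SOFA | Only with a urinary pathogen and a sufficient score |

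If the same man also has dysuria, he is a systemic UTI in the outcome section. His status there turns on the bladder symptom alone.

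**2. The plan's own figure.** Inputs: 1.35% and 1.22%, margin 0.05, one-sided alpha 0.05 (90% interval), power 0.80.

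n = [p_c(1−p_c) + p_t(1−p_t)] × (1.645 + 0.842)² / [0.05 − (p_t − p_c)]²

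= (0.01332 + 0.01205) × 6.18 / 0.0513² ≈ 59.6, so 60 per arm. The stated size reproduces and this point does not affect it.

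**3. Expected events.** 60 × 1.22% = 0.73 and 60 × 1.35% = 0.81 per arm.

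**4. Effect of one case.** Upper 90% bounds for Group A (no prophylaxis) minus Group B, 60 per arm. Wald: d + 1.645 × √[p_A(1−p_A)/60 + p_B(1−p_B)/60]. Newcombe: d + √[(u_A − p_A)² + (p_B − l_B)²], where u and l are Wilson limits.

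| Events A v B | Newcombe | Wald |
|---|---|---|
| 0 v 0 | 4.31% | – |
| 0 v 1 | 2.84% | – |
| 1 v 0 | 7.13% | 4.39% |
| 1 v 1 | 5.62% | 3.84% |
| 2 v 0 | – | 7.15% |
| 2 v 1 | – | 6.35% |

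Losing one Group A case:

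- Newcombe: 1 v 0 to 0 v 0 moves 7.13% to 4.31%; 1 v 1 to 0 v 1 moves 5.62% to 2.84%. Both cross 5%.
- Wald: 1 v 0 and 1 v 1 already pass. The crossing is at 2 v 0 to 1 v 0 (7.15% to 4.39%) or 2 v 1 to 1 v 1 (6.35% to 3.84%).

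Losing one Group B case moves the bound the other way: 1 v 1 to 1 v 0 raises Newcombe from 5.62% to 7.13% and Wald from 3.84% to 4.39%.

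**5. Systematic under-counting (illustration).** Assumption: a share m of infections is missed equally in both arms, and the true rates sit at the margin, 1.35% + 5 points = 6.35% against 1.35%. The observed difference is then 5(1−m) points. Exact binomial probability of declaring non-inferiority:

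| m | Observed difference | Newcombe | Wald |
|---|---|---|---|
| 0 | 5.0 points | 3.7% | 10.7% |
| 20% | 4.0 points | 6.4% | 19.1% |
| 40% | 3.0 points | 11.7% | 33.2% |

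The protocol gives no value for m. The 10.7% at m = 0 belongs to the Wald interval at these low rates, not to the outcome definition; only the rise down each column bears on this point.

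**The case against.** The case against has four parts, and much of it limits the point.

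- **A reader might infer that the febrile man counts nowhere.** The documents do not support that as a general statement. The checklist under Data to be gathered and the first UTI definition in the Background both include fever and flank pain. Sepsis is part of the primary outcome, and the SIRS-type definition could capture culture-positive men. He is lost altogether only if the outcome section is applied literally and no sepsis definition is met.
- **A reader might infer that Follow-up procedures also requires lower urinary symptoms.** Its sentence says that such symptoms with fever are an infection; it does not say that nothing else is. Its non-event rules concern men who stay asymptomatic and mild, self-limiting symptoms, and a man with rigors fits neither.
- **The verdict change depends on the interval method and the arm.** This is correct. Data Analysis specifies an interval for a difference in proportions without a formula that settles Newcombe or Wald, and a case lost from Group B works against non-inferiority.
- **This is one part of a wider lack of a single case definition.** That is also fair. But harmonising urine findings, time windows and sepsis criteria would not remove this condition if the outcome section's wording were kept.

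The direct contradiction remains: one term, one named source and two case sets, with the narrower one defining the primary outcome.

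**Conclusion.** The point holds as a contradiction in the primary-outcome definition. Taken literally, Description of Outcome Measures excludes systemic infection without bladder symptoms from UTI, while the Background counts it under the same EAU classification. Such a man enters the primary outcome only through a sepsis definition that needs a urinary pathogen, or if another section's UTI definition is applied.

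The expected bias is towards non-inferiority, provided that the missed share is similar in both arms and the true rate is higher without prophylaxis. Its size cannot be stated, because the protocol gives no share of such presentations; the 20% and 40% rows are illustrations. With under one expected event per arm, one uncounted Group A case can reverse the conclusion, at 1 v 0 or 1 v 1 under Newcombe and at 2 v 0 or 2 v 1 under Wald. It would be too strong to say that any lost case reverses the result, or always does so in favour of omitting prophylaxis.

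**What to change.** Before outcomes are classified:

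1. Reconcile the Background definitions, Data to be gathered, Follow-up procedures and Description of Outcome Measures into one case definition for the primary outcome.
2. In Description of Outcome Measures, remove localized symptoms as a necessary condition, so that systemic UTI matches the EAU classification reported in the Background.
3. In Follow-up procedures, state that the sentence on lower urinary symptoms with fever does not limit which cases count for the outcome. That sentence also governs treatment, and its treatment content should stay unchanged.

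The cost is a few sentences; the sample size is unaffected. The downside is that some fevers of other origin will need a judgement on source, made by an assessor blinded to allocation. The definitions quoted above contain no such source criterion, so it would be an addition and should be written down as one.

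### The primary outcome excludes mild urinary symptoms only if they resolve on their own, which cannot be seen in an afebrile man given an antibiotic, so his event status can follow the decision to treat

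*Protocol*

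**What the plan says.** Under Description of Outcome Measures, "Primary outcome is the incidence of Urinary tract infection and Sepsis". The same section gives two UTI categories. For the first, "Localized UTI is defined as having symptoms of Dysuria, Urgency, Frequency, Incontinence, and Pressure or cramping in the lower abdomen"; no urinalysis, culture, severity or duration is required. For the second, "Systemic UTI is defined by the presence of localized symptoms plus one of the following: Fever or hypothermia", followed by further systemic signs. It then excludes: "Mild, and Self-limiting lower urinary tract symptoms such as hematuria and dysuria which spontaneously resolves will not be assessed as urinary tract infection". No time limit for resolution is set, and nothing is said about a man who is treated.

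Other sections also bear on who is an event:

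- **Follow-up procedures** has a similar exclusion without the word spontaneous: "Mild and self limiting lower urinary tract symptoms, and hematuria will not be recorded as urinary tract infection". Its positive rule requires persistent and severe symptoms with fever. Its negative rule is "Patients who remain asymptomatic after the 30th post operative day will be treated as not having a post procedural infection".
- **Background Information and Brief Literature Review** requires symptoms together with pyuria and/or bacteriuria. Later in that section, post-biopsy infection is limited to 2 weeks, whereas Follow-up procedures uses 30 days.
- **Criteria for withdrawing subjects and stopping the study** says that men with urinary or systemic symptoms "will be evaluated right away initially with a complete blood count, urinalysis, and urine culture". Those who meet the UTI criteria are counted as infectious complications, but the section does not say which criteria. It also ends the study on counts of mild (more than 2) and severe (more than 1) infections in the experimental group.

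On treatment, the text before the outcome section states: "For patients with mild symptoms which may be treated as outpatient, a budget of 10,000 pesos per patient will be given". Follow-up procedures also admits men whose diagnosis is uncertain and starts antibiotics in them.

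**The concern.** Dysuria is both a defining symptom of localized UTI and an example of an excluded symptom. What separates event from non-event is therefore the undefined word mild and a fact about the later course, namely that the symptoms went away unaided. An antibiotic removes the chance to observe that fact. Two men with the same symptoms and the same urine findings could be scored differently because one was treated and the other was not.

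Either way of resolving the doubt has a price. If treated mild symptoms count, ordinary after-effects of biopsy may enter both arms as UTIs and the trial loses power. If they do not count, true early UTIs that the antibiotic cured drop out of the count. With so few events expected, the non-inferiority conclusion can turn on one such man.

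**Working it through.** **1. One man, all the rules.** Take an afebrile man who reports mild dysuria and frequency within 30 days, has urinalysis and culture, is given an antibiotic and becomes symptom-free.

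| Rule | His status |
|---|---|
| Outcome Measures: symptoms alone, unless mild and spontaneously resolved | Event, unless spontaneous resolution is shown; it cannot be shown |
| Follow-up: mild and self-limiting symptoms excluded | Same difficulty: self-limiting cannot be judged under treatment |
| Follow-up: persistent, severe, febrile symptoms are an infection | Not met, so a non-event |
| Follow-up: asymptomatic through day 30 is no infection | Does not apply; he had symptoms |
| Background criteria, if these are what the stopping section means | Event or non-event, depending on pyuria or bacteriuria |

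The same man left untreated, with symptoms that cleared, is a non-event under Outcome Measures. Only the treatment differs.

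**2. The plan's own figure.** Inputs from Sample Size and Sampling Technique: 1.35% with prophylaxis, 1.22% without, margin 5 points, 80% power, 90% interval (one-sided 0.05).

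n = (1.645 + 0.842)² × [0.0135 × 0.9865 + 0.0122 × 0.9878] / (0.05 + 0.0013)² = 59.6, rounded up to 60 per group.

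The stated 60 is reproduced and is not in dispute here. Expected events are 60 × 0.0122 = 0.73 (no prophylaxis) and 60 × 0.0135 = 0.81 (prophylaxis). One man moves an arm by 1/60 = 1.67 points.

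**3. Effect of one re-scored man.** Data Analysis cites a recommendation for the interval but writes out no formula. I take the simple interval:

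upper = p₁ − p₂ + 1.645 × √[p₁(1 − p₁)/60 + p₂(1 − p₂)/60]

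At 2 v 0: 0.0333 + 1.645 × √(0.0333 × 0.9667/60) = 0.0333 + 0.0381 = 7.15%.

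| Events, experimental v control | Simple upper bound | Newcombe upper bound |
|---|---|---|
| 0 v 0 | 0.00% | 4.31% |
| 1 v 0 | 4.39% | 7.13% |
| 2 v 0 | 7.15% | 9.58% |
| 1 v 1 | 3.84% | 5.62% |
| 2 v 1 | 6.35% | 8.05% |
| 2 v 2 | 5.39% | 6.63% |

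With the simple interval, one more experimental event turns a pass into a fail from 1 v 0 to 2 v 0 and from 1 v 1 to 2 v 1. With Newcombe's, the switch comes from 0 v 0 to 1 v 0.

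**4. Effect on power, by assumption.** Suppose that scoring treated mild symptoms as UTI adds q points to the event rate in both arms. The documents give no value for q. Exact enumeration over all outcomes with 60 per arm, at rates 1.22% + q and 1.35% + q:

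| q (assumed) | Power, simple | Power, Newcombe |
|---|---|---|
| 0 | 84% | 55% |
| 2 | 52% | 36% |
| 5 | 34% | 28% |
| 10 | 25% | 22% |

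**The case against.** The strongest case against has five parts.

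- **Men with fever can be scored.** The outpatient antibiotic text in Follow-up procedures describes fever with urinary symptoms, which is a systemic UTI whether treated or not. The budget sentence may be shorthand for that group, and the outcome section says that mild symptoms rarely need treatment. This stands as a limit: the problem is confined to afebrile men, and how many would be treated is unknown. It does not remove the problem, because the budget sentence carries no fever condition and the uncertain-diagnosis route also leads to antibiotics.
- **A rule does exist.** A reader might infer that these men have no score at all. The documents do not support that, since the Background criteria with the stopping section offer a laboratory-based route. The defect is an unobservable condition among conflicting rules.
- **Late symptoms.** A reader might infer that symptoms starting near day 30 cannot be scored. But the protocol follows men with adverse effects until resolution or stabilization. What remains is the missing time limit for resolution and the conflict between 2 weeks and 30 days.
- **Haematuria.** It is tempting to size the problem by the 14.5% haematuria rate under Ethical Considerations. That figure does not measure it: Follow-up procedures excludes haematuria, and it is not among the localized-UTI symptoms.
- **Blinding and fragility.** Patients and doctors are meant to be blind to arm, so no difference in scoring between arms is shown. Much of the fragility comes from 60 per arm: Newcombe power is 55% with no mis-scoring at all. Both points stand. The scoring rule adds to a fragility that is already there.

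**Conclusion.** The point holds for a defined group: afebrile men with mild urinary symptoms who receive an antibiotic. For them the outcome section's exclusion cannot be applied, the other sections give conflicting answers, and primary-outcome status can follow the decision to treat.

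The group's size cannot be estimated from the documents, but one man is enough to reverse the conclusion at the event counts this trial expects. If he is in the experimental arm, he may also count toward the mild-infection limit in the termination rule. The power losses shown rest entirely on the assumed q and indicate direction and scale only.

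A reader might go further and infer bias in favour of omitting prophylaxis. With treatment decisions meant to be blinded, the documents support only an unstable count and a possible loss of power. This should be corrected, because it lies in the primary outcome and the remedy is cheap.

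**What to change.** Reconcile the UTI rules in Background, the stopping section, Follow-up procedures and Description of Outcome Measures into one event definition with one time window. It should not depend on treatment or later course, so spontaneous resolution and self-limiting should be removed as scoring conditions.

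Score each man whose symptoms begin up to day 30 on his symptoms plus the urinalysis and culture already required at his first report, from samples taken before any antibiotic. The protocol's own Background criterion would serve: symptoms together with pyuria and/or bacteriuria, each at one threshold stated in advance. Use culture-positive cases only as a sensitivity analysis. Making a positive culture the primary criterion would be narrower than the Background definition and is debatable. Apply the same definition to the termination count.

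This concerns scoring only, not who is treated or how.

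The cost is protocol wording and one form field giving the sample date and time relative to the first antibiotic dose. The small downside is that pyuria after a biopsy may be non-specific, which the culture-based sensitivity analysis addresses.
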